5.4.2 Compliance to IMP

Subject's compliance to the IMP will be checked throughout the trial by the investigator. It will be based on the dispensation and retrieval of medication and subjects' records in treatment diary.

Subjects will record their tablet intakes in the treatment diary.

The subject's overall treatment compliance according to eCRF records will be assessed by the tablet count and will be calculated according to the following formula:

$$\text{Overall Compliance (eCRF) (\%)} = \frac{\text{Number of tablets dispensed} - \text{Number of tablets returned}}{\text{Overall treatment duration}} \times 100\%.$$

Tables

No.	Name	Analysis set	Comments
Table 15.1.20.1.1	Compliance to Investigational Medicinal Product	Safety	Default summary statistics for overall treatment compliance according to eCRF records will be presented. Data of centers 104 and 120 will be excluded.

Listings

No.	Name	Analysis set	Comments
Listing 16.2.1.15	Treatment Compliance According to Drug Accountability	Enrolled	Treatment compliance will be listed for the subjects from ES.

5.5 Efficacy Analysis

Primary and secondary efficacy analysis will be based on calculations of the PI in several different cases for non-breastfeeding women. The general formula of PI is

$$PI(<\text{set of cycles}>) = \frac{\sum \text{on-drug pregnancy} \in \{<\text{set of cycles}>\}}{\#\{<\text{set of cycles}>\}} \times 1300.$$

A two-sided 95% CI for the PI will be calculated assuming that events of pregnancy have a Poisson distribution. The CI will be calculated using the following equations from Gerlinger et al. [4]:

$$CI_{lower}(PI(<\text{set of cycles}>)) = \frac{1300}{\#\{<\text{set of cycles}>\}} \times CI_{lower}(\#\{\text{pregnancy} \in \{<\text{set of cycles}>\}\}),$$

$$CI_{upper}(PI(< set of cycles >)) \\ = \frac{1300}{\#\{< set of cycles >\}} \times CI_{upper}(\#\{pregnancy \in \{< set of cycles >\}\}),$$

where

$$CI_{lower}(\#\{pregnancy \in \{< set of cycles >\}\}) \\ = 0.5\chi^2(0.025; 2 \times \#\{pregnancy \in \{< set of cycles >\}\}),$$

$$CI_{upper}(\#\{pregnancy \in \{< set of cycles >\}\}) \\ = 0.5\chi^2(0.025; 2 \times \#\{pregnancy \in \{< set of cycles >\}\} + 1),$$

where $\chi^2(\alpha; n) = \alpha$ -Quantile of χ^2 -distribution with parameter n .

The following information from Pregnancy Notification forms will be taken:

- Subject ID number
- Estimated date of conception
- Method(s) Used to Estimate Conception Date

Efficacy analysis definitions

Term	Definition
Confirmed pregnancy	Subject reported a positive urine home pregnancy test and the pregnancy was confirmed by qualitative urine pregnancy test (β -hCG) and quantitative serum pregnancy test (β -hCG).
Suspected, non-confirmed pregnancy	Subject reported a positive urine home pregnancy test but confirmatory qualitative urine pregnancy test (β -hCG) and/or quantitative serum pregnancy test (β -hCG) are missing.
Suspected, subject confirmed not pregnant	Subject reported a positive urine home pregnancy test but confirmatory qualitative urine pregnancy test (β -hCG) and/or quantitative serum pregnancy test (β -hCG) are negative.
On-drug pregnancy	An on-drug pregnancy includes all conceptions that occur from Day 1 (the initiation of study medication) through seven days after the final tablet (active or placebo) is taken.
Method failure pregnancy*	All on-drug pregnancies of women who used the IMP correctly. Pregnancies are to be excluded from the calculation if in medication cycles of conception or in the previous medication cycles depending on the date of conception: 
 - not all active tablets are taken (based on returned medication, recordings in the e-diary and non-compliance based on DRSP levels, if necessary) - there is an active tablet free interval between the previous medication cycle and the medication cycle of conception. Tablet free interval will be determined by record from treatment diary. - vomiting or diarrhea is documented - administration of prohibited prior or concomitant therapy as detailed in Section 10.7 of the Clinical Trial Protocol is documented
Exposure cycles	28-day cycles, where at least one treatment diary entry of IMP intake is available. In addition, a cycle will be an exposure cycle if the subject become pregnant during this cycle regardless this cycle was a 28-day cycle or not.
Evaluable cycle	Cycles are exposure cycles with intercourse without back-up contraceptive at least once per cycle based on electronic diary question 'Did you have sexual

	
intercourse since the beginning of the cycle?" and answered with: 'Yes I had sexual intercourse without additional contraception'.
 
Also, cycle is to be defined as evaluable if:
 
 - Subject became pregnant at the respective cycle regardless back-up contraception was used or not. - Cycle has missing answer about intercourse or answered "I had NO sexual intercourse at all" but subject became pregnant at the respective cycle. 
Cycle will not be defined as evaluable if subject did not become pregnant and:
 
 - The question was answered with 'Yes I had sexual intercourse with additional contraception'. - Cycles with NO intercourse. - Cycle has missing answer about intercourse.
Perfect cycle*	
Evaluable cycles which have no:
 
 - >48h tablet free interval during the second IMP intake till day 24 of each cycle or >144h interval between the last IMP intake and the first IMP intake in consecutive cycles. Tablet free interval calculation will not take into account cycle days 25-28. - 4 or more days with forgotten tablets intake during 1-24 cycle days. - Protocol deviations having effect on this cycle.

* Method failure pregnancies will be only those which occurred during the perfect cycles, e.g., if pregnancy will contradict method failure definition then the cycle in which pregnancy occurred could not be called perfect cycle and vice versa.

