2.2 Trial Endpoints

2.2.1 Primary Efficacy Endpoints

The primary efficacy endpoint will be the Pearl Index (PI) based on evaluable cycles in non-breastfeeding women aged ≤ 35 years (at the time of trial enrolment).

PI = number of pregnancies*1300/number of evaluable medication cycles

An evaluable cycle is a cycle with intercourse without back-up contraceptive at least once per month based on the electronic diary question 'Did you have sexual intercourse since the beginning of the cycle?' and will be included in the primary analysis. If the cycle is not evaluable but the subject became pregnant in this cycle, the cycle has to be included in the analysis.

Pregnancies following premature termination of IMP will be excluded from the calculations if the estimated date of conception occurs later than seven days after the last tablet intake (active or placebo).

Date of conception will be determined by using the following information:

1. Ultrasound (the date of conception must be based on the most accurate method i.e. the first trimester ultrasound. Subsequent ultrasounds will not be allowed to change dating based on this initial assessment).
2. Ultrasound (in case the first trimester ultrasound was not performed)
3. Quantitative β -hCG
4. Qualitative urine β -hCG determination
5. Estimation of gestational age based on pelvic and/or abdominal examination or pregnancy outcome
6. Investigator's estimation in the absence of the above criteria

Medication cycle will be defined as 28 days starting with the administration of the first tablet from the blister containing 28 tablets and ending with the last day of intake.

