2.6 Sample Size

At least 920 subjects will be allocated to treatment to have at least 5000 evaluable cycles for the PI calculation in non-breastfeeding women aged ≤ 35 years (at the time of trial enrollment). Additionally, a minimum of 75 subjects aged > 35 years will be allocated to treatment. The calculations are based on empirical values including firstly a rate of 24.8% of subjects using back-up contraception or not having intercourse. Secondly, 45% of subjects are assumed to drop out of the trial. The prime target is to collect at least 5000 evaluable cycles.

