5.5.1 Primary Efficacy Analysis

Analysis of the primary efficacy variable defined as PI based on evaluable cycles in non-breastfeeding women aged ≤ 35 years will be performed for the MFAS.

$$PI \text{ (evaluable cycles)} = \frac{\sum \text{on-drug pregnancy} \in \{\text{evaluable cycles}\}}{\#\{\text{evaluable cycles}\}} \times 1300.$$

Respective two-sided 95% CI for PI based on evaluable cycles will be calculated according to formula in Section 5.5.

Tables

No.	Name	Analysis set	Comments
Table 15.2.1.1.1	Pearl Index Based on Evaluable Cycles in Non-Breastfeeding Women Aged ≤ 35 Years (Only Confirmed Pregnancies, Excluding Sites 104 and 120)	Modified Full analysis	Number and percentage of confirmed on-drug pregnancies in the evaluable cycles will be presented. Number of evaluable cycles as well as PI and two-sided 95% CI will be presented. Table analysis will be based on MFAS. Data of centers 104 and 120 will be excluded.

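### The upper 95% limit for the Pearl Index uses the wrong chi-square quantile and degrees of freedom, so with one or more pregnancies the interval lies entirely below its own estimate

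*SAP*

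**What the plan says.** SAP 5.5 states the intended interval: "A two-sided 95% CI for the PI will be calculated assuming that events of pregnancy have a Poisson distribution". Limits are found for the count of pregnancies and then multiplied by 1300 divided by the number of cycles.

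- The lower limit for the count begins "0.5\chi^2(0.025; 2 \times \#\{pregnancy \in \{< set of cycles >" and closes there, so it has 2x degrees of freedom, where x is the number of pregnancies.
- The upper limit is "0.5\chi^2(0.025; 2 \times \#\{pregnancy \in \{< set of cycles >\}\} + 1"), so it has 2x + 1 degrees of freedom and the same 0.025.
- The notation is defined directly underneath: "\chi^2(\alpha; n) = \alpha$ -Quantile of" the chi-square distribution with parameter n.

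SAP 5.5.1 ties the primary endpoint to this: "Respective two-sided 95% CI for PI based on evaluable cycles will be calculated according to formula in Section 5.5". SAP 5.5.2 does the same for the overall, method-failure and evaluable-cycle indices. The protocol synopsis promises a two-sided 95% Poisson interval but gives no formula, so SAP 5.5 is the only specification in the documents.

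**The concern.** A two-sided 95% interval leaves 2.5% in each tail, so the lower limit needs a 0.025 quantile and the upper limit a 0.975 quantile. The SAP uses 0.025 for both. The exact Poisson upper limit also has 2(x + 1) = 2x + 2 degrees of freedom, and the SAP has 2x + 1, as if a bracket around x + 1 had been lost. A smaller gap is that at x = 0 the lower-limit formula has zero degrees of freedom and the SAP gives no rule for that case. Zero events is plausible in women over 35, for whom the plan requires only 75 subjects.

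The trial has no control group. The upper limit of the primary Pearl Index is therefore the main statement of how poor efficacy could be. A programmer or independent validator who follows the SAP to the letter would report an interval that excludes its own point estimate, in every Pearl Index output with at least one pregnancy.

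**Working it through.** **Inputs**

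- Scaling, SAP 2.2.1: "PI = number of pregnancies*1300/number of evaluable medication cycles".
- Denominator, SAP 2.6: "The prime target is to collect at least 5000 evaluable cycles". I use 5000, so the multiplier is 1300/5000 = 0.26. The plan's own assumptions support that figure approximately: 920 × 13 × (1 − 0.248) × (1 − 0.45) = 4947.
- Number of pregnancies x: not given in the documents. I treat it as an assumption and show a range.

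**Formulas, with χ²(p; n) the lower-tail p-quantile as the SAP defines it**

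- Lower limit, printed and exact alike: 0.26 × 0.5 × χ²(0.025; 2x)
- Upper limit, printed: 0.26 × 0.5 × χ²(0.025; 2x + 1)
- Upper limit, exact Poisson: 0.26 × 0.5 × χ²(0.975; 2x + 2)

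For x = 15 the printed limits for the count are 8.395 and 8.769. Multiplied by 0.26 these become 2.18 and 2.28. The estimate is 15 × 0.26 = 3.90.

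| x (assumed) | Pearl Index | As printed | Exact Poisson | Upper limit if only 0.025 is changed to 0.975 |
|---|---|---|---|---|
| 1 | 0.26 | 0.007 to 0.028 | 0.007 to 1.45 | 1.22 |
| 5 | 1.30 | 0.42 to 0.50 | 0.42 to 3.03 | 2.85 |
| 10 | 2.60 | 1.25 to 1.34 | 1.25 to 4.78 | 4.61 |
| 15 | 3.90 | 2.18 to 2.28 | 2.18 to 6.43 | 6.27 |
| 20 | 5.20 | 3.18 to 3.28 | 3.18 to 8.03 | 7.87 |

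The printed upper limit for the count is below x for every x from 1 to 2000, so the reversal does not depend on the assumed count. It does not depend on the number of cycles either, which only rescales the estimate and both limits.

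**Zero events.** The printed upper limit is 0.00049 pregnancies; the exact limit is 3.69. At 5000 cycles these are Pearl Indices of about 0.0001 and 0.96. The printed limit is then not below the estimate of 0, but it is useless as a bound. For women over 35 the denominator would differ and the index limits would rescale accordingly.

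**Coverage.** Poisson probabilities were summed at mean counts 1, 3, 5, 8, 10, 15, 20 and 25. The printed interval covers the true mean 0%, 2.2%, 1.8%, 1.7%, 1.3%, 0%, 0% and 0% of the time. The stated 95% is not reproduced. The exact interval covers between 95.5% and 98.8% at the same means.

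**Other readings tried, at x = 10 (Pearl Index 2.60)**

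- Only the bracket was lost, so the 0.025 quantile has 2(x + 1) degrees of freedom: the upper limit is 1.43, still below the estimate.
- 0.025 means an upper-tail probability in both lines: the interval is 4.44 to 4.61, entirely above the estimate, and this reading contradicts the SAP's own definition.
- Only the quantile is wrong (0.975 with 2x + 1): the upper limit is 4.61. It lies above the estimate but is lower than the exact 4.78.

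No single meaning of 0.025 makes both lines correct.

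**The case against.** The strongest reply is that this is a transcription slip. The SAP attributes the equations to a published recommendation on Pearl Index intervals and states the 95% intention plainly. It prints no code for these limits, and an interval that excludes its own estimate would be noticed in the first output. The programs may well be right already. That is possible and cannot be settled from the documents. If so, the specification and the output disagree, and the SAP still needs correcting.

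The degrees of freedom are a fair point of dispute. The SAP promises a Poisson interval but never calls it exact, and half the 0.975 quantile with 2x + 1 degrees of freedom is the Jeffreys upper limit. However, the SAP pairs it with a lower limit on 2x degrees of freedom, which is the exact form, so a lost bracket is the likelier explanation. The effect is small next to the quantile error: 6.27 against 6.43 at 15 events, though 0.65 against 0.96 at zero events. With only the quantile repaired, the upper-tail error is 5.0% at a mean of 3, 4.0% at 5 and 2.9% at 10, but 1.4% at 8, 1.8% at 15 and 2.2% at 25. It exceeds 2.5% at some means and not at others.

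Two further limits stand. The Kaplan-Meier cumulative pregnancy rates in SAP 5.5.2 have their own 95% limits and do not use this formula, so the Pearl Index limit is not the only bound on failure. And the documents available state no acceptance threshold for the upper limit, so no pass or fail consequence can be shown.

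**Conclusion.** The concern holds. As specified, the upper limit for the primary and secondary Pearl Indices is not an upper limit, and with at least one pregnancy the interval excludes its own estimate. At 5000 cycles and 15 pregnancies the reported upper limit would be 2.28 instead of 6.43, around an estimate of 3.90. Coverage is 0% to 2.2% at the means checked, against 95% stated.

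The event counts are assumptions, but the reversal holds for every count from 1 to 2000 and any number of cycles. The wrong quantile causes it. The wrong degrees of freedom are a second, smaller error that matters most at very low counts. The conclusion rests on the SAP's own 95% statement and its definition of the quantile, not on the cited source, which was not available. Because it affects the primary analysis, it must be corrected.

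**What to change.** In SAP 5.5, replace the upper limit for the count by 0.5 × χ²(0.975; 2x + 2), writing the degrees of freedom as 2 × (x + 1) so that the bracket cannot be lost again. Keep the lower limit as it is, and add that it equals 0 when x = 0. Name the interval as the exact Poisson interval. Apply the corrected formula to every Pearl Index table and figure, and confirm that the production and validation programs match it.

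The cost is one line of SAP text and at most one line of code, with no new data and no change to the point estimates. If the printed formula has been programmed, the reported upper limits will rise; if the programs already use the exact form, no result changes.

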6 Urinalysis: leukocytes, nitrite, protein, glucose, ketones, blood, pH, urobilinogen, bilirubin, hemoglobin – dipstick.

7 V1a: Height has to be determined for all subjects. V1b to V6: Height has only to be determined in adolescent subjects (i.e. < 18 years of age).

8 In addition, each subject will perform a urine dipstick pregnancy test at home at the beginning of each new medication cycle. In case of an equivocal or positive urine pregnancy test, a quantitative serum pregnancy test has to be performed for confirmation.

9 On Day 10 + 2 days of each cycle, the subjects will be called by the site staff to collect information on adverse events which might have occurred, and to confirm e-diary compliance. Throughout each cycle, subjects will be called by site staff to review e-diary compliance as needed.

10 Only electrolytes.

11 Measurements of vital signs will be repeated twice with a break of one minute between them at each visit in sitting position, after at least five minutes of rest. The subject should not talk.

12 Two blood samples per visit will be collected to determine plasma concentrations of LF111 at Visits 2 and 4 and should ideally be one hour apart (between 45 and 120 minutes after the first sample) without a LF111 administration in between.

13 The subject will be asked if she has a wish of pregnancy at each visit. In case of a positive answer, the subject will be discontinued.

14 Once the e-diary has been assigned to a subject, a practice diary (training section in e-diary) has to be actively completed.

15 The investigator should arrange for the subject's further contraceptive treatment or make an appropriate referral, as needed, at V5. Consecutive contraceptives should be started after last IMP intake and should be used at least until V7/Follow-up. This arrangement is outside the trial and costs will not be covered by the Sponsor.

16 The subject will be asked by the investigator: Are you satisfied with this method? Answer options: strongly agree, agree, undecided, disagree, strongly disagree, no answer. Furthermore, for women who switched from another oral contraceptive method to the IMP will be asked by the investigator: How was your wellbeing during the intake of the IMP in comparison to the time when you took your former oral contraceptive? Answer options: better, unchanged, worse, no answer.

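### The SAP's definition of a confirmed pregnancy is narrower than the primary Pearl Index numerator, so a serum-positive on-drug pregnancy can be left out of the primary table

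*SAP*

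**What the plan says.** The numerator is described in two ways.

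- **All on-drug pregnancies.** SAP 2.2.1 gives "PI = number of pregnancies*1300/number of evaluable medication cycles". The formulas in 5.5 and 5.5.1 sum on-drug pregnancies, and 5.5 explains: "An on-drug pregnancy includes all conceptions that occur from Day 1 (the initiation of study medication) through seven days after the final tablet". No test result is required.
- **Confirmed pregnancies only.** For Table 15.2.1.1.1, the only table in 5.5.1, the SAP says: "Number and percentage of confirmed on-drug pregnancies in the evaluable cycles will be presented". The definitions table in 5.5 reserves the word confirmed for cases where "Subject reported a positive urine home pregnancy test and the pregnancy was confirmed by qualitative urine pregnancy test" and by quantitative serum testing as well. The three conditions apply jointly.

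Section 5.5 has two further categories, and each also starts from a reported positive home test. Suspected, non-confirmed applies when the confirmatory urine test, the serum test or both are missing. "Suspected, subject confirmed not pregnant" applies when either or both are negative.

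On testing, footnote 8 of the visit schedule says that "each subject will perform a urine dipstick pregnancy test at home at the beginning of each new medication cycle". This is in addition to the clinic urine tests scheduled from V1b to V7. The same footnote requires a quantitative serum test after any positive or equivocal urine test, and it does not limit this to home tests.

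**The concern.** The formula and the table in 5.5.1 do not count the same events. The table's definition depends on how a pregnancy came to light, not only on whether it was established. A woman with a positive serum test and a conception inside the on-drug window belongs in the numerator under 2.2.1, yet she may fail the confirmed definition because of a urine result or because she reported no positive home test.

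This affects the primary endpoint, and the error has one direction: an omitted pregnancy can only lower the PI and make the contraceptive look better. The same restriction runs through the rest of the efficacy output. All 18 efficacy tables without the _add suffix are limited to confirmed pregnancies.

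**Working it through.** **1. Classify every serum-positive on-drug pregnancy under 5.5 as written.** Cross the home test (reported positive or not) with the confirmatory urine test (positive, negative, missing). This gives 2 × 3 = 6 patterns.

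| Home test | Confirmatory urine | Category in 5.5 | Table 15.2.1.1.1 | Confirmed-and-suspected tables |
|---|---|---|---|---|
| positive | positive | confirmed | in | in |
| positive | negative | confirmed not pregnant (route b) | out | out |
| positive | missing | suspected, non-confirmed (route c) | out | in |
| no positive report | positive, negative or missing (3 patterns) | none (route a) | out | out |

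One pattern of six reaches the primary table and two reach the wider tables. These are counts of patterns, not of women. The wider version exists in 12 _add tables and recovers route (c) only.

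**2. Can route (a) arise under the schedule?** Yes. Home tests fall at the start of each new cycle. Clinic urine tests fall around Day 20 of cycles 1, 3, 6 and 9, at V6/EDV and at V7. A woman who conceives in her last cycle, or in the seven days after her last tablet, starts no further cycle and so has no later scheduled home test. V6/EDV or V7 is then the scheduled occasion that would find the pregnancy. Earlier in treatment a clinic test may also come first, but the next home test may still turn positive and be reported.

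**3. Size per omitted case.** Inputs are the multiplier of 1300 (2.2.1) and the target of 5000 evaluable cycles (2.6).

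The planning figures roughly reproduce that target. With 920 subjects, 45% dropout and 24.8% using back-up or having no intercourse, and dropouts contributing nothing, 920 × 13 × 0.55 × 0.752 = 4947 cycles, 1.1% below 5000. If dropouts contribute 6.5 cycles on average (assumption), the total is 920 × 13 × 0.775 × 0.752 = 6970.

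The fall in PI per omitted pregnancy is 1300/N:
- N = 4947: 0.263
- N = 5000: 0.26
- N = 6970: 0.19

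**4. Illustration at 5000 cycles.** The documents give no expected number of pregnancies, so the counts are assumptions. The limits are exact Poisson: 0.5·χ²(0.025; 2x) and 0.5·χ²(0.975; 2x+2), each times 1300/N.

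| On-drug pregnancies | PI, none omitted (95% CI) | PI, one omitted (95% CI) |
|---|---|---|
| 10 | 2.60 (1.25–4.78) | 2.34 (1.07–4.44) |
| 15 | 3.90 (2.18–6.43) | 3.64 (1.99–6.11) |

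The upper limit falls by about 0.33 per omission (4.78 − 4.44 = 0.34; 6.43 − 6.11 = 0.32). I used the standard upper limit. The one printed in 5.5 takes the 0.025 quantile and would give 2.28 for 15 pregnancies, below the estimate itself; that is a separate matter.

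**The case against.** The strongest reply is that the SAP already provides a route for awkward cases. Section 3.3 sends all subjects who became pregnant to the data review meeting (Listing DRM01), asks it to assign each pregnancy to a category and to settle open SAP issues, and has its decisions documented. The listings also show every on-study pregnancy. This stands as far as traceability goes, and it would be wrong to infer that cases are settled without a record. But the meeting assigns cases to the categories in 5.5, and those categories are the fault. Nothing written in advance tells it to depart from them.

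Other parts of the reply also stand:

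- Route (c) is an analysis choice with a planned companion (Tables 15.2.1.4.4_add and 15.2.1.4.5_add). It is the weakest of the three.
- Route (b) needs an unusual set of results, and a category whose label contradicts a positive serum test. The either-or wording nevertheless puts the case there.
- Section 5.5 sets no time limit for the home report, so a later positive home test would satisfy it. One cannot infer that every end-of-treatment conception is lost, or put a figure on that loss.
- The list in 2.2.1 that ends with the investigator's "estimation in the absence of the above criteria" is for dating conception. It cannot be read as a rule on what confirms a pregnancy. Nor does footnote 8 state that serum alone suffices for the efficacy category.
- A reader might add that the denominator uses a different concept, since a cycle is evaluable if "Subject became pregnant at the respective cycle regardless back-up contraception was used or not". That has no practical weight: one cycle in 5000 changes a PI of 3.90 by less than 0.001.

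**Conclusion.** The wording is wrong as it stands and should be corrected. Sections 2.2.1 and 5.5.1 define the primary numerator as all on-drug pregnancies, and the primary table applies a narrower definition. Routes (a) and (b) lead to omission from the primary PI and from its wider version. Route (c) leads to omission from the primary PI only.

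The effect is 0.26 PI points per omitted pregnancy at 5000 evaluable cycles, always downwards. A reader might infer that the reported PI is biased or that the conclusion would change. The documents do not support this: they give no pregnancy counts, target PI or margin, and the number of affected women may be zero. The conclusion concerns the written rule. It rests on a literal reading of 5.5 and on the protocol synopsis; confirmation steps elsewhere in the protocol and the data review report were not available to check.

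**What to change.** In 5.5, define a confirmed pregnancy as any on-drug pregnancy with a positive quantitative serum β-hCG, or with ultrasound or pregnancy-outcome evidence, however it was first detected and whatever the urine result, including a missing one. Limit the confirmed-not-pregnant category to women with a negative quantitative serum test and no such positive evidence. The suspected category then takes the remaining positive home tests. Use this definition for Table 15.2.1.1.1, and bring 2.2.1, footnote 8 and 5.5.1 into line with it.

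The cost is rewording. The test results and pregnancy outcomes are already collected and listed, and the tables are already planned. The primary PI may come out slightly higher, and pregnancies already assigned to a category must be rechecked. The data review meeting follows database lock in an open-label trial, so this is a late change to a primary numerator. The reason should be documented and the PI under the old wording shown beside the new one.
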